Communication with external partners, including the SPCG network, are planned if necessary to increase accrual through wider collaboration.

A prerequisite of the trial is that all Danish radiotherapy (RT) centres are able to join with most patients with locally or locally advanced disease offered inclusion (72, 73). The impact of an unexpected heterogeneity according to the individual department’s equipment will be minimised by performing the randomisation with stratification on the centre. In addition, the dosimetric performance of each center’s technical implementation will be vetted during the trial as described the RT-QA program, cf. Appendix A.

Patients

Inclusion criteria:

- Patients with biopsy verified PCa with no distant metastases with either
- Intermediate- or high-risk PCa, defined as at least one of the following risk criteria:
 - Clinical stage cT2c-T3b (UICC TNM 8th edition)
 - Imaging stage, T3a or T3b
 - \geq Gleason score 4+3, (ISUP Grade groups 3,4 or 5)
 - Regional lymph node metastases N1
- Age > 18
- WHO score 0-1
- Intraprostatic lesion visible on MRI
- Suitable for focal boost
- Ability to give written informed consent and willingness to return for follow-up

Exclusion Criteria:

- WHO performance status ≥ 2
- If, for any patient related reason, an MRI cannot be performed
- T4
- International prostate symptom score (IPSS) ≥ 20

- If fiducial markers cannot be inserted
- TURP within 3 months from start of treatment
- Previous pelvic irradiation
- If the patient is judged by the physician to be unable to adhere to trial activities
- History of chronic inflammatory bowel disease (CIBD)

Treatment related procedures

- Neoadjuvant and adjuvant endocrine treatment according to Danish national guidelines, which currently includes 3 months LHRH agonist or antagonist before the start of RT. Abiraterone treatment for 2 years is allowed for participants with either N1 disease or two or three of the following criteria: Gleason score 8 – 10, PSA > 40 ng/ml, T3-4.
- MRI prostate and PSMA-PET/CT or PSMA-PET/MRI before the start of endocrine treatment.
- Planning with fiducial markers according to institutional protocol, MRI and PSMA-PET/ CT according to imaging guidelines in this protocol.
- Bladder and rectum according to institutional protocol
- Contouring and target definition according to guidelines in this protocol: boost, prostate, seminal vesicles, pelvic lymph nodes.

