- Dose constraints for organs at risk are kept according to guidelines in this protocol
- Guidelines for IGRT according to institutional protocol.
- Treatment is delivered with institutional protocols that fulfil the goals and constraints given in this protocol (appendix B).

Radiotherapy

Radiotherapy planning:

Modern RT planning is wholly dependent on high level computing. This allows for creation of highly personalised dose plans with several different dose levels within the same plan. Additionally, these plans exhibit sharp dose gradients towards critical organs at risk (OAR). Depending on treatment modality plans will either use a simultaneously integrated or sequential boost. In the former case the treatment session delivers a boost to the intraprostatic lesion (if randomised for boost) in addition to the prescribed doses to prostate and elective targets. In the latter case prescribed doses to prostate and elective targets are delivered in the same treatment sessions whereas a boost will be delivered in separate sessions using specialised equipment e.g. an MR-Linac. In either case the dose planning will seek to minimise the trade-off between sufficient target coverage - usually between 95% and 107% of the prescribed target doses - and reducing as much as possible the doses to OAR. It is not uncommon that requirements for target and OAR doses are mutually exclusive. The order in which every dose requirement should be prioritised is detailed in Appendix B as well as specific

requirements to target coverage. To ensure that the dose planning of all participating centres will be vetted as part of the comprehensive RT-QA program described in Appendix A.

Rectal and bladder preparation protocol:

Patients should be treated with a comfortably filled bladder and an empty rectum/bowel according to local protocol. Use of Image Guided Radiotherapy (IGRT) is mandatory to ensure the elective target coverage and to assess bladder- and rectal filling. Application of a bladder-filling protocol in an attempt to decrease the volume of bladder irradiated is recommended using IGRT to check the target positioning.

Target volume definition, dose and fractionation:

Delineation of the targets are performed on the treatment planning MRI, guided by both the diagnostic multiparametric MRI (mpMRI) and PSMA-PET CT scan. Organs at risk (OARs) are delineated on the planning CT scan.

Fractionation:

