- 20 fractions, no boost: Prostate and seminal vesicles: 60 Gy/ 20 fractions. Pelvic: 45 Gy /20 fractions.
- 20 fractions, boost: Boost 75 Gy/20 fractions, prostate and seminal vesicles: 60 Gy/ 20 fractions. Pelvic: 45 Gy /20 fractions.
 - If a boost is delivered on special equipment, such as an MR accelerator, it is allowed to give the boost in fewer fractions with same equivalent dose and maintaining same overall treatment time
- 12 fractions, no boost: Prostate and seminal vesicles: 50 Gy/ 12 fractions, Pelvic: 37 Gy /12 fractions.
- 12 fractions, boost: Boost 60 Gy/12 fractions, prostate and seminal vesicles: 50 Gy/12 fractions, Pelvic: 37 Gy /12 fractions.
 - If a boost is delivered on special equipment, such as an MR accelerator, it is allowed to give the boost in fewer fractions with same equivalent dose and maintaining same overall treatment time

All treatments with 5 fractions per week

Intraprostatic lesion(s): If a boost is to be performed, the most dominant lesion(s) are contoured as GTVp_FB_post with the prefix 1, 2 etc. according to the number of lesions with the use of information from the planning MRI and PSMA-PET/CT used as guidance. As the lesions and the prostate gland normally decrease in size with neoadjuvant ADT, a CTVp_FB_final should be created. This volume should not only include the GTVp_FB_post but also account for the potential initial tumor volume (GTVp_FB_pre) as observed on the diagnostic MRI performed prior to initiating ADT. The three sequences used from mpMRI are:

- 1) T2 weighted image, where the tumour lesions appear in grey
- 2) DWI (Diffusion Weighted Imaging), where the tumour lesions appear as white areas
- 3) ADC (Apparent Diffusion Coefficient), where the tumour lesions appear as black areas

CTVp_FB should be included in the CTVp or CTVp_SV. No margin is used for intraprostatic lesions.

For radiation target nomenclature, see appendix C

Prostate: MRI is used to contour the CTVp volume as the whole gland with any visible extracapsular extension of disease included.

Elective pelvic lymph nodes: If N1, elective lymph nodes should be delineated according to NRG Oncology Updated International Consensus Atlas on Pelvic Lymph Node Volumes for Intact and Postoperative Prostate Cancer, 2021 (74). Elective pelvic lymph node area is named CTVn_E. Any clinically suspicious lymph nodes should be included in the CTVn_E. PTV is derived by adding a 5-10mm margin to CTVp, CTVp_SV and CTVn_E. See appendix D

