Before enrolling patients in the protocol, each participating centre must complete a validation "dummy run" to verify the accuracy of the delivered dose. This validation requires dose planning on a test case with a delineation of a focal boost, along with patient-specific QA measurements for the delivered dose. Centres may use their standard patient-specific QA devices for these measurements, which involve two evaluations: (a) a general assessment of the total dose delivered and (b) a precise evaluation of the dose delivered specifically to the prostate area, including the focal boost, with stereotactic accuracy (91).

QA measurements should follow AAPM Task Group 218 methodologies (92), such as:

- Conducting IMRT QA measurements using True Composite (TC) or Perpendicular Field-by-Field (PFF) if TC is unsuitable,
- Analysing dose measurements against the corresponding dose plan doses in absolute dose mode, using a threshold for excluding low-dose areas,
- Variations of the detector response as well as of the accelerator output should be factored out of the analysis.

To pass the dummy run, QA analysis must achieve:

- A $\geq 95\%$ pass rate for $\gamma_{3\%,2\text{mm}}$ with a 10% dose threshold for overall dose evaluation,
- A $\geq 95\%$ pass rate for $\gamma_{3\%,1\text{mm}}$ with a 10% dose threshold specifically for the prostate area including the focal boost (stereotactic accuracy).

Different QA approaches may be used for these two evaluations, and each centre must submit a documentation of its QA procedure as well as a detailed evaluation of the test case to the QA group.

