Appendix B: Dose constraints

Table 1 below shows isotoxic dose constraints to organs at risk. The Equivalent Dose at 2 Gy fractions known from the conventional 39-fraction treatment regime have been converted to equivalent doses for the two hypo-fractionated schemes using an α/β -value of 3.

Requirements for target coverage for the two hypo-fractionated schemes are listed in table 2. Both tables include priorities designating in which order specific constraints should be fulfilled in case of conflicts between target and OAR. CTVs and certain OARs both have priority 1. This should not lead to conflicts since there are no overlaps between the two.

Table 1

OAR	Normo-fractionated DVH constraint	EQD2 of physical dose	Isotoxic dose: 20 fractions ($\alpha/\beta = 3$)	Isotoxic dose: 12 fractions ($\alpha/\beta = 3$)	Priority
Rectum	$V_{75\text{Gy}} < 2\text{cm}^3$	74 Gy	60 Gy	50 Gy	1
	$V_{70\text{Gy}} < 10\%$	67 Gy	55 Gy	46 Gy	3
	$V_{50\text{Gy}} < 60\%$	43 Gy	46 Gy	31 Gy	3
Urethra	$D_{0.1\text{ccm}} < 85\text{Gy}$	88 Gy	71 Gy	59 Gy	1
	$D_{1\text{ccm}} < 80\text{Gy}$	81 Gy	65 Gy	54 Gy	1
Bowel Bag	$D_{\text{max}} < 78\text{Gy}$	78 Gy	63 Gy	53 Gy	1
Bowel Bag - PTV_5mm	$V_{30\text{Gy}} < 450\text{cm}^3$	23 Gy	20 Gy	18 Gy	3
	$V_{45\text{Gy}} < 195\text{cm}^3$	37 Gy	32 Gy	28 Gy	3
Bladder	$D_{\text{mean}} < 62\text{Gy}$	57 Gy	47 Gy	40 Gy	3
	$V_{80\text{Gy}} < 15\%$	81 Gy	65 Gy	54 Gy	3
	$V_{70\text{Gy}} < 35\%$	67 Gy	55 Gy	46 Gy	3
Femoral Heads	$D_{2\%} < 55\text{Gy}$	48 Gy	41 Gy	35 Gy	3
Body (outside PTVs)	$D_{2\%} < 83\text{Gy}$	85 Gy	67 Gy	56 Gy	3

Table 2

Target volume (X denoting specific dose scheme)	DVH constraint		Priority
	20 fractions	12 fractions	
GTVp_FB_post_X	$D_{\text{mean}} = 75 \text{ Gy} (\pm 1\%)$	$D_{\text{mean}} = 60 \text{ Gy} (\pm 1\%)$	2
GTVp_FB_post_X	$V_{71.25\text{Gy}} > 99.5\%$	$V_{57\text{Gy}} > 99.5\%$	2
CTVp_FB_final_X	$V_{71.25\text{Gy}} > 95\%$	$V_{57\text{Gy}} > 95\%$	3
CTVp_FB_final_X	$D_{0.1\text{ccm}} > 80.25\text{Gy}$	$D_{0.1\text{ccm}} > 64.2 \text{ Gy}$	3
CTVp_X	$V_{57\text{Gy}} > 99.5\%$	$V_{47.5\text{Gy}} > 99.5\%$	1
CTVp_SV_X (T3b)	$V_{57\text{Gy}} > 99.5\%$	$V_{47.5\text{Gy}} > 99.5\%$	1
CTVp_SV_X ($\leq T3a$)	$V_{42.75\text{Gy}} > 99.5\%$	$V_{35.15\text{Gy}} > 99.5\%$	1
CTVn_E_X	$V_{42.75\text{Gy}} > 99.5\%$	$V_{35.15\text{Gy}} > 99.5\%$	1
PTVp_X	$V_{57\text{Gy}} > 98\%$	$V_{47.5\text{Gy}} > 98\%$	2
PTV_SV_X (T3b)	$V_{57\text{Gy}} > 98\%$	$V_{47.5\text{Gy}} > 98\%$	2

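### The boost near-maximum row in Appendix B, Table 2 (CTVp_FB_final D0.1ccm) is printed as a minimum at exactly 107% of prescription, so its sign appears reversed

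*Protocol*

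**What the plan says.** Table 2 of Appendix B lists the target requirements for the two schedules. For CTVp_FB_final it has two rows, both priority 3. The first is a coverage row: more than 95% of the volume must receive 71.25 Gy (20 fractions) or 57 Gy (12 fractions). The second concerns the hottest 0.1 ccm: "D_{0.1\text{ccm}} > 80.25\text{Gy" in the 20-fraction column and "D_{0.1\text{ccm}} > 64.2 \text{ Gy" in the 12-fraction column.

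The Radiotherapy planning section describes "sufficient target coverage - usually between 95% and 107% of the prescribed target doses" and sends planners to the appendix for the details: "The order in which every dose requirement should be prioritised is detailed in Appendix B as well as specific" requirements for coverage.

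The same metric appears in only one other place in Appendix B, the urethra row of Table 1, where it is a cap: "D_{0.1\text{ccm}} < 85\text{Gy".

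The boost volume in question is not the GTV alone. Under Target volume definition, dose and fractionation, the text on CTVp_FB_final says: "This volume should not only include the GTVp_FB_post but also account for the potential initial tumor volume" seen before androgen deprivation.

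**The concern.** A D0.1ccm requirement is a statement about the hot spot. Written with a greater-than sign it demands a hot spot; written with a less-than sign it limits one. The threshold sits exactly at the top of the protocol's usual dose range, and nothing in the document asks for a dose peak above 107% inside the lesion. A plan that does what the planning text describes is therefore marked deficient by the table to which that text refers.

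What is at stake is consistency of peak boost dose in the two boost arms. One centre may follow the row as printed while another silently reads it as a cap. With the sign as printed, Table 2 also gives no upper limit on the boost volume against which a reviewer could reject a plan.

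**Working it through.** **Inputs.** Boost prescriptions of 75 Gy in 20 fractions and 60 Gy in 12 fractions (Target volume definition, dose and fractionation); D0.1ccm thresholds of 80.25 and 64.2 Gy, and coverage doses of 71.25 and 57 Gy on the same volume (Appendix B, Table 2); usual range 95-107% (Radiotherapy planning).

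**Step 1: where the thresholds come from.**

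- Upper end: 1.07 × 75 = 80.25 Gy and 1.07 × 60 = 64.2 Gy. Both equal the printed D0.1ccm thresholds exactly.
- Lower end: 0.95 × 75 = 71.25 Gy and 0.95 × 60 = 57 Gy. Both equal the printed coverage doses exactly.

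The two CTVp_FB_final rows thus carry the two ends of the 95-107% range. They describe that range only if the second row is an upper limit.

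**Step 2: what each sign does to a plan.** The two example plans are illustrative.

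| Hottest 0.1 ccm | 20 fractions | 12 fractions | Row as printed | Sign turned |
|---|---|---|---|---|
| 105% of prescription | 78.75 Gy | 63.0 Gy | fails | passes |
| 110% of prescription | 82.5 Gy | 66.0 Gy | passes | fails |

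**Step 3: size of the literal demand.** 80.25 − 75 = 5.25 Gy and 64.2 − 60 = 4.2 Gy above prescription, in physical dose.

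**Step 4: do other rows set the limit instead?**

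- Every other one-sided row of Table 2 is a lower coverage bound at 95% of its prescription: 57/60, 47.5/50, 42.75/45 and 35.15/37 are all 0.95. None limits a peak.
- The GTVp_FB_post mean row (75 or 60 Gy, ±1%, priority 2) fixes an average: 74.25 to 75.75 Gy, or 59.4 to 60.6 Gy. It restrains hot spots but does not state a maximum, and it covers the GTV rather than the whole of CTVp_FB_final.
- The priority 1 limits for urethra, rectum and bowel in Table 1 restrain the peak where those organs are close. The urethra D0.1ccm limit is 71 Gy (20 fractions) or 59 Gy (12 fractions), below the thresholds in question.

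**Step 5: would the quality assurance detect it?** The dummy-run pass rule rests on "Analysing dose measurements against the corresponding dose plan doses in absolute dose mode", so it tests whether the plan was delivered, not whether the planned peak is sensible. The human checks are broader. Each centre submits a detailed evaluation of its test case, the QA group reviews the first boost patient in each schedule before treatment, planning workshops are held, and under Risks and contingency plans each centre's "technical implementation will be vetted during the trial". These may well catch the row, but none of them states a different near-maximum criterion.

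**The case against.** The strongest objection is that the finding rests on one character in a machine-read table. Table 2 contains no less-than sign anywhere, so nothing shows that the reading handled that sign there, and two cells of one row are not independent confirmation. The 13 less-than signs in Table 1 are all plausible as printed, but that is a different table. This stands, and it is why the source PDF must be checked first.

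Second, a medical physicist would probably recognise 107% as a cap and plan accordingly. That is likely, but it means relying on the reader to overrule the printed specification.

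Third, the row has limited force. It is priority 3, it cannot justify a breach of a priority 1 organ limit or of the priority 2 GTV mean, and the QA group reviews plans before the first treatments. This also stands and lowers the severity. In addition, the planning text says that 95-107% is usual, not absolute, so a deliberate minimum hot spot is logically possible. Nothing in the document supports one.

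A reader might go further and infer that peak boost dose is uncontrolled, for example by assuming a GTV volume and working out how high 0.1 ccm could go while the mean stays within 1%. The documents do not support that. They give no GTV volumes, such a calculation needs the rest of the GTV to lie exactly at 95%, and the organ limits still apply. A reader might also convert the excess to EQD2 with the alpha/beta of 3 in Appendix B. That value is stated there for organ-at-risk constraints, and for the boost it gives figures that disagree with the 110 Gy EQD2 in the overall design table.

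**Conclusion.** The concern holds as an internal inconsistency in the treatment specification: as printed, the row contradicts the planning text that refers to it, and Table 2 lacks an explicit near-maximum limit for the boost volume. The literal demand is a hottest 0.1 ccm more than 5.25 Gy (20 fractions) or 4.2 Gy (12 fractions) above prescription.

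For scale only, the target EQD2 values in the design table imply an alpha/beta of roughly 1.5: 60 × (3 + 1.5)/3.5 = 77.1 Gy against the stated 77 Gy. On that assumption the excess is about 14 Gy EQD2: 126.4 − 112.5 = 13.9 Gy in 20 fractions and 125.6 − 111.4 = 14.2 Gy in 12.

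Severity is minor to should-fix. The row is low priority, stronger limits and plan review stand above it, and the same scaled row applies in both boost arms. The documents do not show that either factorial comparison is biased or that patients would receive unsafe doses. Sample size, power, alpha and endpoints are untouched. The conclusion assumes that the sign in the source PDF is as read here; confidence is medium for that reason.

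**What to change.** Check the row in the source PDF. If the sign is as read here, change it to D0.1ccm < 80.25 Gy (20 fractions) and D0.1ccm < 64.2 Gy (12 fractions), notify the centres, and re-check any test-case or boost plans already made against the printed row. If a minimum was intended, say so, give the reason, and add a separate near-maximum limit for CTVp_FB_final.

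The cost is a one-row correction, a notice to centres and a short plan review. Randomisation, endpoints and sample size do not change. If the PDF already shows an upper limit, no action is needed.

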Appendix C: Radiation target nomenclature

Target	Delineation	GTV nomenclature	CTV nomenclature	PTV According to local guidelines	Doses	Number of fractions
Intraprostatic lesion(s) if boost is performed (prior to initiating ADT)	Based on MRI +/- PSMA-PET CT signals	GTVp1_FB_pre* GTVp2_FB_pre* etc.	N/A	N/A	N/A	N/A
Intraprostatic lesion(s) if boost is performed (post initiating ADT)	Based on MRI +/- PSMA-PET CT signals	GTVp1_FB_post_75 GTVp2_FB_post_75 etc. GTVp1_FB_post_60 GTVp2_FB_post_60 etc.	CTVp1_FB_final_75 CTVp2_FB_final_75 etc. CTVp1_FB_final_60 CTVp2_FB_final_60 etc.	N/A	75 Gy 60 Gy	20 fx 12 fx
Prostate	MRI used for volume definition		CTVp_60 CTVp_50	PTVp_60 PTVp_50	60 Gy 50 Gy	20 fx 12 fx
Seminal Vesicles - if invasion (T3b)	Based on the MRI and adjusted according to location on the CT scan		CTVp_SV_60 CTVp_SV_50	PTVp_SV_60 CTVp_SV_50	60 Gy 50 Gy	20 fx 12 fx
Seminal Vesicles - no invasion (≤ T3a)	The proximal 2 cm of vesicles		CTVp_SV_45 CTVp_SV_37	PTVp_SV_45 PTVp_SV_37	45 Gy 37 Gy	20 fx 12 fx
Elective pelvic lymph nodes	According to NRG Oncology Updated International Consensus Atlas on Pelvic Lymph Node Volumes		CTVn_E_45 CTVn_E_37	PTVn_E_45 PTVn_E_37	45 Gy 37 Gy	20 fx 12 fx

Abbreviations: GTV: Gross Tumour Volume; CTV: Clinical Target Volume; PTV: Planning Target Volume; Gy: Gray; fx: Fractions

* There are no dose constraints for the GTV(s) defined prior to initiating ADT. This/these volume(s) should be included in the CTV(s) for the intraprostatic lesion(s).

[figure not shown]
Appendix D: Guideline for elective pelvic lymph node radiotherapy

[figure not shown]
DAPROCA 10 core group encourages all investigators to have a clear strategy for elective pelvic lymph node irradiation and to adhere to this strategy consistently during the trial. Below are the core groups' suggestions for a strategy for elective pelvic lymph node radiation. The indication for lymph is based on the risk group of the patient and the available imaging used for detection of lymph node metastases with either conventional imaging (CT and bone scan) or PSMA PET/CT. The below guidelines are divided in two sections based on either conventional imaging or PSMA PET/CT.

The indication for pelvic lymph node radiotherapy are in accordance with the current DAPROCA guidelines and are based on the BRIGANTI 2019 nomogram and the BRIGANTI 2023 nomogram for estimating the risk of lymph node involvement (LNI). Both nomograms are depicted in the figures below illustrating the suggested cut-offs of either 7% or 5% (18,19).

[figure not shown]
The guideline introduces the term "true pelvis", which includes the pelvic lymph nodes up to the L5/S1 junction and the "pelvis" which is the "true pelvis" plus the common iliac nodes. The figure below is copied and modified from the study of Lawton et al (74) showing the consensus contours. The "true pelvis" is in cyan and the "pelvis" includes both the cyan and blue volumes.

The "pelvis" with the inclusion of common iliac lymph nodes should only be used if the patient has N1 disease as the common iliac lymph nodes are a secondary drainage area that is rarely involved without lymph node metastases in the "true pelvis".

[figure not shown]

[figure not shown]
DAPROCA 10 GUIDELINE - CONVENTIONAL IMAGING FOR LN MET

[figure not shown]
BRIGANTI 2019 nomogram conventional imaging for LN metastases

DAPROCA 10 GUIDELINE - PSMA PET/CT FOR LN MET

[figure not shown]
BRIGANTI 2023 nomogram for patients N0 on PSMA PET/CT

Appendix E: Guideline for seminal vesicle radiotherapy

Radiotherapy to the seminal vesicles are being performed quite differently throughout Denmark. The DAPROCA10 core group suggests the below strategy to be used in the trial for consistency and improved outcomes of the trial, where precision of the radiotherapy is a key factor. Imaging of seminal vesicle involvement (SVI) is optimally performed with a combination of multiparametric MRI and PSMA PET/CT and the proposed strategy is dependent on the use of contemporary prostate cancer imaging. SVI rarely occurs without the involvement of the “midbase” of the prostate gland, as the cancer spreads along the ejaculatory ducts or as extraprostatic extension into the seminal vesicles. In a study of prostate cancer specimens, the percentage of seminal vesicle invasion with and without “midbase” invasion was 78% and 0.7%, respectively (93,94).

[figure not shown]
Pattern of spread- Ohori’s classification

In an often referred publication from Kestin et al the median length of SVI was 1 cm with a 90% percentile of 2 cm, forming the basis for including the proximal 2 cm of the seminal vesicles as an elective target (95).

Below are three examples illustrating when and how the seminal vesicles are to be included as a target.

No elective irradiation of seminal vesicles

[figure not shown]

Tumour does not involve base of prostate gland

Little risk of SVI

No elective SV volume

[figure not shown]
Elective irradiation of seminal vesicles

Tumour involves base of prostate gland

Include proximal 2 cm of seminal vesicles bilaterally as elective target

Irradiation of seminal vesicles

Tumour involves left SV on MRI/PET

[figure not shown]
Include GTV of involved seminal vesicle in focal boost volume if randomised for boost

The remaining SV volume included in 50 or 60 Gy volume

Contouring of seminal vesicles

Delineate CTV SV on both planning CT (blue) and MRI (red)

Create ITV SV from the sum of both volumes (yellow) and subtract the part of the ITV SV extending into rectum (brown)

References

1. de Crevoisier R, Bayar MA, Pommier P, Muracciole X, Pêne F, Dudouet P, et al. Daily Versus Weekly Prostate Cancer Image Guided Radiation Therapy: Phase 3 Multicenter Randomized Trial. *Int J Radiat Oncol Biol Phys.* 2018;102(5):1420–9.
